### 8.2.5 Change from Baseline

Change from baseline can only be calculated for measures that have baseline and post-baseline records and will be calculated as:

- Value at respective visit – baseline value.

Percentage change from baseline will be calculated as:

- (change from baseline / baseline value) \* 100

If either the baseline or the visit value is missing, the change from baseline and percentage change from baseline will be missing as well.

### 8.2.6 Multiple Assessments

All data will be reported according to the nominal visit date at which it was assessed (that is, no visit windows will be applied during dataset creation and the visit will not be re-allocated if the actual visit date deviates from the planned date according to the visit schedule in the

protocol). If multiple assessments for the same visit occur, it will be distinguished why this is the case. If a laboratory sample was repeated due to technical problems the results from the valid sample(s) for this visit will be used in the analysis. If a laboratory sample was repeated as safety follow-up to monitor abnormal values of the initial sample, the initial sample (revealing the abnormal values) of this visit will be used in the analysis.

Data from all assessments (scheduled and unscheduled), including multiple assessments, will be included in listings.

### 8.2.7 Actual Treatment

The subject's actual treatment will be derived from exposure data. If a subject is either up-titrated or down-titrated during Treatment Period 2, the actual treatment will be the initial treatment until dose change and the modified treatment after dose change. The subject will be reported in the initial treatment until dose change and in the modified treatment beginning with the dose change. If a subject receives a treatment different from the planned it will be decided during the Data Review Meeting on an individual base what is considered the actual treatment.

### 8.2.8 Study Periods Relative to Treatment

The following definitions for the evaluation periods of efficacy and safety will be used to define the durations used in the denominator of the time-normalized endpoints and safety endpoints such as exposure and subject-years. It is not intended to re-assign assessments made during scheduled visits based on these definitions. Scheduled visits will not be re-labelled based on subject's study days irrespective of whether the visit takes place in the planned time window.

The Study Completion Date Visit in this study is at the end of Treatment Period 1 or Treatment Period 2 or at the time of premature study discontinuation. This visit is followed by the Follow-up Visit which may be waived in place of a telephone contact.

**Efficacy Analysis:** The evaluation periods will be:

**Run-in Period (all subjects):** From Week 1 Day 1 of the Run-in Period until the date / time of the Week 1 Day 1 Visit of Treatment Period 1 (the date / time of the first administration of

investigational product in Treatment Period 1) or the Study Completion Visit date and time (whichever occurs earlier). The duration (days) of the Run-in period will be:

Week 1 Day 1 Visit date and time of Treatment Period 1 or Study Completion Visit date and time – Week 1 Day 1 Visit date and time of Run-in + 1.

**Treatment Period 1 (subjects who receive an IV loading dose of investigational product):** From Week 1 Day 6 Visit of Treatment Period 1 (the date / time of the first SC administration of investigational product in Treatment Period 1) until the date / time of the Week 13 Day 91 Visit (the date / time of the first administration of investigational product in Treatment Period 2) or the Study Completion Visit date and time (whichever occurs earlier). The duration (days) of the efficacy evaluation period for Treatment Period 1 will be: Week 13 Day 91 Visit date and time or Study Completion Visit date and time – Week 1 Day 6 Visit date and time + 1.

**Treatment Period 1 (CCI [REDACTED]):** From Week 3 Day 15 Visit of Treatment Period 1 (the date / time of the second SC administration of investigational product in Treatment Period 1) until the date / time of the Week 13 Day 85 Visit (the date / time of the first administration of investigational product in Treatment Period 2) or the Study Completion Visit date and time (whichever occurs earlier). The duration (days) of the efficacy evaluation period for Treatment Period 1 will be: Week 13 Day 85 Visit date and time or Study Completion Visit date and time – Week 3 Day 15 Visit date and time + 1.

**Treatment Period 2 (subjects assigned to [REDACTED] mg CSL312 and FXII/PLG HAE subjects):** Treatment Period 2 will start after it is assumed that all subjects have achieved steady-state under CSL312. From Week 21 Day 147 Visit of Treatment Period 2 (the date / time of the third administration of investigational product in Treatment Period 2) until the date / time of the Study Completion Visit. The duration (days) of the efficacy evaluation period for Treatment Period 2 will be:

Study Completion Visit date and time – Week 21 Day 147 Visit date and time + 1.

**Treatment Period 2 (C1-INH HAE subjects assigned to [REDACTED] mg CSL312):** Treatment Period 2 will start after it is assumed that all subjects have achieved steady-state under CSL312.

- [REDACTED] mg portion: From Week 21 Day 147 Visit of Treatment Period 2 (the date / time of the third administration of investigational product in Treatment Period 2) until the

date / time of the Study Completion Visit OR the date / time of the planned dose reduction to [REDACTED] mg (following Amendment 2), whatever occurs first. The duration (days) of the efficacy evaluation period for [REDACTED] mg in Treatment Period 2 will be:  
(Study Completion Visit date and time or Date and time of planned dose reduction, whichever occurs first) – Week 21 Day 147 Visit date and time + 1;

- **[REDACTED] mg portion:** From the date / time of the planned dose reduction to [REDACTED] mg (following Amendment 2) until the Study Completion Visit date / time. The duration (days) of the efficacy evaluation period for [REDACTED] mg in Treatment Period 2 will be: Study Completion Visit date and time – Date and time of planned dose reduction.

**Treatment Period 1 and 2 (subjects who receive an IV loading dose of investigational product and who participate in Treatment Period 2):** From Week 1 Day 6 Visit of Treatment Period 1 (the date / time of the first SC administration of investigational product in Treatment Period 1) until the date / time of the Study Completion Visit or the date / time of planned dose reduction, whichever occurs first. The duration (days) of the efficacy evaluation period for Treatment Period 1 and 2 will be:

Study Completion Visit date and time or Date and time of planned dose reduction, whichever occurs first – Week 1 Day 6 Visit date and time + 1.

After planned dose reduction, data will not be included in the summary tables.

HAE attacks with start dates outside the above specified efficacy evaluation periods will not be included in the efficacy analysis but will only be listed:

- HAE attacks with a start date between the first and second administrations of the investigational product in Treatment Period 1,
- HAE attacks with a start date between Week 13 Day 85/91 and Week 21 Day 147,
- HAE attacks with start date between date of last treatment period visit and Follow-up.

**Safety Analysis Exposure:** The duration in days of the evaluation periods will be:

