10.3.2 Efficacy Analyses

10.3.2.1 Primary Efficacy Analysis

10.3.2.1.1 The Primary Analysis

The primary endpoint (time-normalized number of HAE attacks) will be analyzed using the ITT and PP Populations. The ITT population will be used for the primary analysis and the PP will be used as the secondary analysis.

The evaluation periods for efficacy, including for the time-normalized number of HAE attacks are specified in [Section 10.3](#). For the primary analysis, only the efficacy period for Treatment Period 1 and subjects with q4wk dosing, as defined in [Section 10.3](#), is applicable.

Subjects are to enter HAE symptoms into their eDiary. HAE attacks are based upon review of patient diaries and review of relevant interim medical history by the investigator, including hospital / medical records and any information provided by the subject. Using medical judgment, the investigator is to determine the occurrence of an HAE attack.

The time-normalized number of HAE attacks per month during treatment is calculated per subject as: [the number of HAE attacks / length of subject treatment in days] * 30.4375, where the length of subject treatment is calculated for Treatment Period 1 as: [the date / time of the first SC dose of investigational product in Treatment Period 2 – the date / time of the first SC dose of investigational product in Treatment Period 1].

The time-normalized number of HAE attacks will be summarized descriptively by median (primary) and mean (secondary) with corresponding 95% CIs by treatment (ie, placebo, or [REDACTED] mg, [REDACTED] mg, or [REDACTED] mg CSL312 q4wk).

To test for a difference in the primary efficacy endpoint between [REDACTED] mg CSL312 q4wk or [REDACTED] mg CSL312 q4wk and placebo, pairwise comparisons will be performed by testing the hypotheses using a two-sided Mann-Whitney Test.

To account for multiple testing, the alpha level of 5% will be evenly split between the hypotheses tested. Therefore, the [REDACTED] mg CSL312 q4wk or [REDACTED] mg CSL312 q4wk CSL312 doses (in subjects with C1-INH HAE) will each be evaluated against placebo at $\alpha = 0.025$ for each test:

$$H01: a1 = 0 \text{ vs } H11: a1 \neq 0$$

and

$$H02: a2 = 0 \text{ vs } H12: a2 \neq 0$$

In the above hypotheses, the term “a1” is the shift between the 2 distributions of [REDACTED] mg CSL312 q4wk and placebo and the term “a2” is the shift between the distributions of [REDACTED] mg CSL312 q4wk and placebo, respectively.

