### 8.2.3 Durations

Durations (e.g., the duration of an AE) will be calculated in days:

- End date and time (if available) – start date and time (if available) + 1.

CCI

To transform durations or CCI which are calculated in days into months, divide the number of days by 30.4375; to transform to weeks divide the number of days by 7; to transform to years divide the number of days by 365.25. These algorithms return decimal numbers and ignore the actual numbers of days in the months or years between start date and stop date. The "year" used in these algorithms is 365.25 days long, and the "month" is one twelfth of that year.

Age will be taken from the data base.

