**Treatment Period 1 (subjects who participate in Treatment Period 2):**

Week 13 Day 85/91 Visit date and time – 1 – date and time of first administration of study treatment + 1.

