### 10.2.1 Analysis of Responders

A subject is classified as a responder if the percentage reduction in time-normalized number of HAE attacks per month is  $\geq 50\%$  as compared to the Run-in Period. The percentage reduction is calculated within a subject as:

$$100 * [1 - (\text{TNA CSL312} / \text{TNA Run-in})]$$

where TNA CSL312 is the time-normalized number of HAE attacks per month during treatment with CSL312 and TNA Run-in is the time-normalized number of HAE attacks per month during the Run-in Period.

The number and percentage of subjects classified as responders and non-responders will be presented along with 95% CI.

CCI

In Treatment Period 2, the comparison between CCI mg and CCI mg CSL312 q4wk will only include data collected prior to the planned dose reduction following Amendment 2.

A by-subject listing will be provided as specified in Section 7 with the response classification and the degree of reduction in time-normalized number of HAE attacks per month.

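### SAP 8.2.8 adds one day to a Treatment Period 1 duration that protocol 10.3.2.1.1 defines as a plain date/time difference, so non-zero attack rates come out about 1.2% low

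*SAP*

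**What the plan says.** Protocol 10.3.2.1.1 gives the primary endpoint as attacks divided by days of treatment, times 30.4375, "where the length of subject treatment is calculated for Treatment Period 1 as" the date/time of the first subcutaneous (SC) dose in Treatment Period 2 minus "the date / time of the first SC dose of investigational product in Treatment Period 1". Nothing is added.

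SAP 10.1 uses the same rate but takes its denominator from SAP 8.2.8. There the Treatment Period 1 duration for subjects with an IV loading dose is the Week 13 Day 91 (or Study Completion) date and time minus "Week 1 Day 6 Visit date and time + 1". The Run-in duration likewise ends in "Week 1 Day 1 Visit date and time of Run-in + 1".

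The added day follows the general rule in SAP 8.2.3: "End date and time (if available) – start date and time (if available) + 1". It is not carried everywhere in 8.2.8:

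- The efficacy portion after the planned dose reduction is "Study Completion Visit date and time – Date and time of planned dose reduction", with no added day.
- Treatment Period 1 safety exposure for subjects who continue is "Week 13 Day 85/91 Visit date and time – 1 – date and time of first administration of study treatment + 1", where the two ones cancel.

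SAP 10.2.1 compares the on-treatment rate with the Run-in rate: "A subject is classified as a responder if the percentage reduction in time-normalized number of HAE attacks per month is" at least 50% below Run-in. SAP section 5, which lists changes to the planned analyses, does not mention the duration formula.

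**The concern.** Adding one is right when whole calendar days are counted inclusively. It is wrong for the difference of two time stamps, which is already the elapsed time; the extra day was not observed. The two documents therefore give different primary-endpoint values from the same data, and a programmer cannot satisfy both.

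The second issue is the responder endpoint, a ratio of two rates. If both denominators were inflated by the same proportion, the error would cancel. They are not, because one day is a larger share of a short Run-in than of Treatment Period 1. In an arm of 8, one reclassified subject moves the responder proportion by 12.5 points.

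**Working it through.** The documents state no figure that depends on the added day, so there is nothing to reproduce first.

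**Inputs**

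- Treatment Period 1 efficacy period, every-4-weeks arms: Day 6 to Day 91 (protocol 10.3), so T = 91 − 6 = 85 elapsed days; the SAP gives 86.
- Run-in length R: at least 28 days (protocol 4.1.3). Entry to Treatment Period 1 should come within 14 days of Day 57, that is by Day 71, or about 70 elapsed days.
- At least 2 Run-in attacks for C1-INH HAE (protocol 4.1.3).
- Planning rates 2.9 and 0.6 attacks per month (SAP 4.5).

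**Step 1: effect on a rate.** With the extra day, a non-zero rate over L elapsed days is multiplied by L/(L + 1).

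| Period | L | L/(L + 1) | Understated by |
|---|---|---|---|
| Treatment Period 1, every 4 weeks | 85 | 85/86 = 0.988 | 1.2% |
| Run-in, minimum | 28 | 28/29 = 0.966 | 3.4% |
| Run-in, 8 weeks | 56 | 56/57 = 0.982 | 1.8% |
| Run-in, about 70 days | 70 | 70/71 = 0.986 | 1.4% |
| Treatment Period 2, Day 147 to Day 399 | 252 | 252/253 = 0.996 | 0.4% |

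In Treatment Period 1, 2.9 per month becomes 2.866 and 0.6 becomes 0.593. A rate of zero stays zero.

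**Step 2: early dropouts.** SAP 8.1.1 treats the every-4-weeks endpoint as missing only for dropout before Day 6, so short periods stay in the analysis. One attack in 2 elapsed days is 30.4375/2 = 15.2 per month by the protocol and 30.4375/3 = 10.1 by the SAP.

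**Step 3: primary test.** In 20,000 simulated trials with 8 per arm, Poisson counts and Treatment Period 1 lengths of 85 ± 3 days, the Mann-Whitney result did not change in any trial.

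**Step 4: responder status.** With r Run-in attacks and a attacks on treatment, reduction = 100 × [1 − (a/T)/(r/R)]. Take R = 28, T = 85, r = 2, a = 3:

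- no added day: 1 − (3 × 28)/(2 × 85) = 1 − 84/170 = 50.6%, responder;
- added day in both periods: 1 − (3 × 29)/(2 × 86) = 1 − 87/172 = 49.4%, non-responder;
- added day in Treatment Period 1 only: 1 − 84/172 = 51.2%, responder.

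The loss therefore comes from the Run-in's extra day outweighing the one in Treatment Period 1.

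**Step 5: how often.** With T = 85 the following (r, a) pairs lose responder status:

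- R = 28: (2,3), (4,6), (6,9) and (8,12);
- R = 30: (5,7);
- R = 34: (4,5);
- R = 35: (5,6);
- R = 36: (6,7).

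No pair examined changes at 42, 49, 56, 63 or 70 days. Next assume Poisson counts, a Run-in rate of 2.9 per month with at least 2 attacks, Run-in length uniform over the stated range and T = 85 ± 6 days. The share of subjects losing responder status is then:

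| Treatment rate per month | Run-in 28–35 days | 28–57 days | 28–71 days |
|---|---|---|---|
| 0.6 | 0.4% | 0.3% | 0.2% |
| 1.0 | 0.9% | 0.6% | 0.4% |
| 1.45 | 1.2% | 0.7% | 0.5% |

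No simulated subject moved the other way. Per arm of 8 this is about 8 × 0.002 = 0.02 to 8 × 0.012 = 0.1 subjects.

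**Step 6: reversal.** For a dropout with T = 10, R = 28, r = 11, a = 2, the reduction is 1 − 56/110 = 49.1% without the extra day and 1 − 58/121 = 52.1% with it. The subject gains responder status.

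**The case against.** **The effect is negligible.** The same formula applies in all four blinded arms, the shift is about 1%, and the test is rank-based. This stands for the primary test.

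**The responder loss is a knife-edge.** A reader might take the 28-day example as typical: with a Run-in of exactly 28.0 days, about 5% of subjects change at 0.6 attacks per month and about 8% at 1.45. The documents do not support that as the general size. With T = 85, three attacks against two is a response without the extra day only if R ≤ 85/3 = 28.33 days. Given the 28-day minimum, that is a window of 8 hours. The Run-in may last 8 weeks or more and ends only at first dosing. This objection stands, and the 0.2% to 1.2% range is the relevant one.

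**The protocol has no Run-in length formula.** Protocol 10.3 gives only its start and end points. This also stands: the explicit contradiction concerns Treatment Period 1, while the responder loss arises from the Run-in formula.

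**The SAP is not inconsistent with itself at the dose reduction.** A reader might infer otherwise because the later portion has no added day. The two portions sum to Study Completion minus Day 147 plus 1, so the extra day is simply not counted twice. That inference should not be drawn.

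**The inclusive day may match the numerator.** SAP 8.2.8 excludes attacks by start date. If that were programmed on dates alone, both boundary dates would count and an inclusive denominator would fit. This does not remove the error: SAP 8.2.8 runs each period from one date/time to another, and the attack listing in SAP 10.1 carries start times. It does show that numerator and denominator must be fixed together.

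**Conclusion.** The point holds as a discrepancy between protocol and SAP on the primary-endpoint denominator, undeclared in SAP section 5. Non-zero Treatment Period 1 rates in the every-4-weeks arms are about 1.2% too low on schedule, and more so after early dropout. The primary test result is practically unaffected.

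For completers the percentage reduction is slightly understated, and occasionally a subject near 50% loses responder status. The estimate of 0.2% to 1.2% of subjects rests on assumed Poisson counts and assumed spreads of Run-in and treatment length, neither of which the documents give for individual subjects.

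Two stronger readings fail. Not every attack rate is understated: zero rates do not move, and the portion after dose reduction has no added day. Nor is the bias in the reduction always downward: it can reverse when Treatment Period 1 is shorter than the Run-in.

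**What to change.** In SAP 8.2.8, delete the added day from every efficacy duration computed from date and time: Run-in, Treatment Period 1, Treatment Period 2 (including the portion before dose reduction) and the combined periods. The Treatment Period 1 denominator then equals the elapsed time in protocol 10.3.2.1.1. The portion after dose reduction needs no edit.

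In SAP 8.2.3, limit the added day to durations computed from whole dates.

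State in SAP 8.2.8 and 10.1 that attacks are included by start date and time, using the same boundaries as the denominator, so that removing the day does not leave a date-based count over a shorter period.

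The cost is a short SAP wording edit and a small programming change, plus a check of how attack inclusion is coded. No new data, sample-size change or protocol amendment is needed.

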C1-INH HAE subjects who continue to participate in Treatment Period 2 will be receiving CSL312 [REDACTED] mg or [REDACTED] mg q4wk SC at the beginning of Treatment Period 2. Effective with Amendment 2, all C1-INH HAE subjects receiving the [REDACTED] mg dose will have their dose reduced to [REDACTED] mg q4wk SC at their next scheduled study visit. FXII/PLG HAE subjects will be maintained on the [REDACTED] mg q4wk SC dose. The first dose of CSL312 in Treatment Period 2 will be administered at the Week 13 (Day 91) Visit and at the Week 13 (Day 85) Visit for subjects who administer investigational product q4wk and q2wk in Treatment Period 1, respectively. Administration of CSL312 at the Week 13 (Day 85 / 91) Visit, the Week 17 (Day 119) Visit, and the Week 21 (Day 147) Visit will be self-administered under supervision of the investigator or delegate at the study site. After administration of the CSL312 at the Week 21 (Day 147) Visit, all subsequent doses of CSL312 will be self-administered SC every 28 days (\pm 2 days) by the subject at home or at the study site.

Subjects should remain at the study site for at least 30 minutes after any CSL312 administration that occurs at the study site.

Dose modification details for Treatment Period^o2 are presented in [Section 5.5](#).

Additional information related to dosing and administration of investigational product is presented in [Section 6.2](#).

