6.1.2 Randomization Procedures

Randomization will be conducted using an IRT. The investigator will be supplied with a user guide for the IRT. The randomization list will be generated according to the approved randomization specifications. The IRT service provider will keep the randomization code on file.

Treatment Period 1

In Treatment Period 1, subjects will be randomized using block randomization with fixed block size by means of centralized IRT to 1 of 4 blinded treatment arms:

- The first 32 subjects with C1-INH HAE who are assigned to treatment in Treatment Period 1 will be randomized in a 1:1:1:1 ratio to receive placebo, [REDACTED] mg CSL312, [REDACTED] mg CSL312, or [REDACTED] mg CSL312 q4wk SC.

Up to 8 additional subjects with C1-INH HAE who are assigned to treatment in Treatment Period 1 after the first 32 subjects (above) will receive [REDACTED] mg CSL312 q2wk SC.

Subjects with FXII/PLG HAE who are assigned to treatment in Treatment Period 1 will receive [REDACTED] mg CSL312 q4wk SC.

Treatment Period 1 will be conducted in a blinded manner for C1-INH HAE subjects who receive placebo, [REDACTED] mg CSL312, [REDACTED] mg CSL312, or [REDACTED] mg CSL312 q4wk. Emergency unblinding will be performed in the IRT ([Section 6.1.3.2](#)).

Treatment Period 1 will be conducted in an open-label manner for C1-INH HAE subjects who receive [REDACTED] mg CSL312 q2wk and for FXII/PLG HAE subjects who receive [REDACTED] mg CSL312 q4wk.

Treatment Period 2

In Treatment Period 2, subjects will be re-randomized using block randomization with fixed block size by means of a centralized IRT to receive either [REDACTED] mg or [REDACTED] mg CSL312 q4wk.

- For subjects with C1-INH HAE, randomization will be stratified by Treatment Period 1 treatment assignments: subjects on placebo q4wk; subjects on [REDACTED] mg CSL312 q4wk; subjects on [REDACTED] mg CSL312 q2wk.
 - Subjects on placebo q4wk in Treatment Period 1 will be randomized in a 1:1 ratio to receive either [REDACTED] mg CSL312 q4wk or [REDACTED] mg CSL312 q4wk in Treatment Period 2.
 - Subjects on [REDACTED] mg CSL312 q4wk in Treatment Period 1, will be randomized in a 1:1 ratio to receive either [REDACTED] mg CSL312 q4wk or [REDACTED] mg CSL312 q4wk in Treatment Period 2.
 - Subjects on [REDACTED] mg CSL312 q2wk in Treatment Period 1 will be randomized in a 1:1 ratio to receive either [REDACTED] mg CSL312 q4wk or [REDACTED] mg CSL312 q4wk in Treatment Period 2.

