- **Treatment Period 1 (subjects who receive an IV loading dose of investigational product and who participate in Treatment Period 2):** From the date / time of the first SC administration of investigational product in Treatment Period 1 (ie, at the Week 1 [Day 6] Visit) until the date / time of the first administration of investigational product in Treatment Period 2 (ie, at the Week 13 [Day 91] Visit).
- **Treatment Period 1 (subjects who receive an IV loading dose of investigational product and who do NOT participate in Treatment Period 2):** From the date / time of the first SC administration of investigational product in Treatment Period 1 (ie, at the Week 1 [Day 6] Visit) until the Week 13 (Day 91) Visit date and time.
- **Treatment Period 1 (CCI [REDACTED]):** From the date / time of the second SC administration of investigational product in Treatment Period 1 (ie, at the Week 3 [Day 15] Visit) until the date / time of the first administration of investigational product in Treatment Period 2 (ie, at the Week 13 [Day 85] Visit).
- **Treatment Period 1 (CCI [REDACTED]):** From the date / time of the second SC administration of investigational product in Treatment Period 1 (ie, at the Week 3 [Day 15] Visit) until the Week 13 (Day 85) Visit date and time.
- **Treatment Period 2 (subjects assigned to CCI mg):** From the date / time of the third administration of investigational product in Treatment Period 2 (ie, at the Week 21 [Day 147] Visit) until the Week 57 (Day 399) Visit date and time.
- **Treatment Period 2 (subjects assigned to CCI mg):**
 - From the date / time of the third administration of investigational product in Treatment Period 2 (ie, at the Week 21 [Day 147] Visit) until the Week 57 (Day 399) Visit date and time OR time point of planned switch to CCI mg (per protocol Amendment 2), whatever occurs first OR
 - From the date / time of planned switch to CCI mg (per protocol Amendment 2) until the Week 57 (Day 399) Visit date and time.

The evaluation period for assessment of efficacy in Treatment Period 2 will be extended to the subject's final Treatment Period 2 visit for subjects who are in the Extended Treatment Period 2.

Hereditary angioedema attacks with a start date between the first and second administrations of the investigational product in Treatment Period 1 will not be included in the analyses of efficacy, but will be presented in a listing (only).

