## 5 Changes in the Conduct of Planned Analyses

Changes after finalization of this SAP will either be described in a protocol amendment or in an update to the SAP. They will be clearly indicated in the CSR.

Changes in the analysis following Amendment 2 are as follows:

Efficacy analysis: the planned treatment for the efficacy analysis is the randomized treatment. Following Amendment 2, for subjects randomized to [REDACTED] mg CSL312 q4wk in Treatment Period 2 their planned treatment will be reduced to [REDACTED] mg CSL312 q4wk. The subjects will be reported under this treatment after the planned dose reduction. For subjects who receive continuously the same dose of CSL312 during both treatment periods, data will be included in the analysis until the planned dose reduction following Amendment 2.

Safety analysis: the actual treatment will be used for the Safety analysis. Subjects with planned or unplanned dose reduction or allowed dose increase will be reported under the treatment they actually received. For subjects who receive continuously the same dose of CSL312 during both treatment periods, data will be included in the analysis until any dose change.

The second and third interim analysis will be combined into one.

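### SAP 8.2.8 gives no valid pre-reduction efficacy window in Treatment Period 2 when the Amendment 2 dose reduction falls at Week 17 or Week 21, and states no rule for those subjects

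*SAP*

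**What the plan says.** **Allocation.** Protocol 6.1.2 keeps the Week 13 allocation for C1-INH HAE subjects: "In Treatment Period 2, subjects will be re-randomized using block randomization with fixed block size by means of a centralized IRT". For example, "Subjects on placebo q4wk in Treatment Period 1 will be randomized in a 1:1 ratio to receive either" one of two doses. Subjects already on either of those doses in Treatment Period 1 continue on it. Protocol 3.1.4 says the same.

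**Reduction.** Protocol 3.2.2 states: "Effective with Amendment 2, all C1-INH HAE subjects receiving the" higher of these doses are reduced at their next scheduled visit. Protocol 5.5 repeats this. SAP 4.3.2 adds that the subject must first have consented to Amendment 2. SAP 5 confirms that the dose concerned is one allocated in this period: for subjects randomized to that "mg CSL312 q4wk in Treatment Period 2 their planned treatment will be reduced to" another dose.

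**Window before the reduction.** SAP 8.2.8 starts it at the Week 21 (Day 147) visit. Its length is Study Completion or "Date and time of planned dose reduction, whichever occurs first) – Week 21 Day 147 Visit date and time + 1". Protocol 10.3 has the same structure, from the third dose of the period until the Week 57 "Visit date and time OR time point of planned switch to" the reduced dose ("per protocol Amendment 2), whatever occurs first OR" a second branch that starts at the switch).

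**Window after the reduction.** SAP 8.2.8 runs it from the reduction to Study Completion. The same section makes attacks that start between Week 13 and Week 21 listing-only.

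**Use.** SAP 10.1 divides the attack count by the window length. SAP 10.2.1 builds the responder classification on that rate and says the Treatment Period 2 dose comparison "will only include data collected prior to the planned dose reduction following Amendment 2".

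**The concern.** The formula assumes that every reduction comes after Day 147, but the reduction rule does not guarantee this. A subject between Week 13 and Week 21 when the amendment reaches them, or one who enters Treatment Period 2 afterwards, can be reduced at Week 17 or Week 21, before or exactly when the window opens.

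Such a subject still attends Week 21 on the reduced dose. Both dates therefore exist and the formula returns a number, unlike for a dropout with no Week 21 visit. SAP 6.2 assigns the ITT population within treatment period by allocated dose, so the subject stays in the column for the dose they have left.

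The per-dose attack rate, responder and attack-free summaries for Treatment Period 2 are at stake, as is the dose comparison limited to pre-reduction data. The arms are small, and Protocol 3.3.1 says the study's data will inform dose selection for a possible phase 3 study.

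**Working it through.** The plan states no length for this window, so there is no figure of its own to reproduce.

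**Inputs**
- Visits after Week 13: Day 119 (Week 17), Day 147 (Week 21), Day 231 (Week 33) and Day 399 (Week 57), from Protocol 8.5.4. Weeks 25 and 29 carry only a pregnancy test, for which a site visit is optional, so Day 231 is taken as the next full visit.
- Rate = attacks / days × 30.4375 (SAP 10.1).
- Responder: 100 × (1 - treatment rate / Run-in rate) is at least 50 (SAP 10.2.1).
- Run-in rate above zero: at least 2 attacks are required (Protocol 4.1.3).
- Planning rates of 0.6 and 2.9 attacks per month, Poisson (SAP 4.5), used in step 3 only as an assumption.

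**1. Pre-reduction window** = min(completion, reduction) - 147 + 1

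| Planned reduction | Length (days) |
|---|---|
| Week 17, Day 119 | 119 - 147 + 1 = -27 |
| Week 21, Day 147 | 147 - 147 + 1 = 1 |
| Week 33, Day 231 | 231 - 147 + 1 = 85 |
| None, completion at Day 399 | 399 - 147 + 1 = 253 |

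At Week 21 the true interval is 147 - 147 = 0. The single day comes only from the added 1, so a check for negative lengths would not catch it.

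**2. The SAP formulas applied literally**
- -27 days: no attack can start both after Day 147 and before Day 119. Rate = 0 / (-27) × 30.4375 = 0. Reduction = 100 × (1 - 0) = 100%, so the subject is a responder and attack-free.
- 1 day, matched by date and time: no attacks, with the same result.
- 1 day, matched by date: one attack on Day 147 gives 1 / 1 × 30.4375 = 30.4 per month. A 50% reduction would then need a Run-in rate of 2 × 30.4375 = 60.9 per month, so in practice the subject is a non-responder.

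**3. How little one day shows.** The chance of no attack in one day is exp(-0.6 / 30.4375) = 98% at 0.6 per month and exp(-2.9 / 30.4375) = 91% at 2.9 per month. Over 253 days at 0.6 per month it is exp(-0.6 × 253 / 30.4375) = 0.7%.

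**4. Reduced-dose portion, Week 17 switch, completion at Day 399.** Denominator = 399 - 119 = 280 days. Listing-only days inside it = 147 - 119 = 28, and 28 / 280 = 10%. At a constant true rate of 0.6 per month, the computed rate would be 0.6 × 252 / 280 = 0.54. A Week 21 switch (399 - 147 = 252 days) has no overlap.

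**5. Combined window for subjects continuing on the same dose.** A Week 17 switch gives 119 - 6 + 1 = 114 days, which is positive.

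**The case against.** - **No passage says these subjects count as attack-free responders.** A reader might infer it from the formulas, but the documents do not state it. SAP 8.1.1 treats the rate as missing when a subject drops out before the Treatment Period 1 window opens, and a programmer might do the same with a negative length. This stands against the strong reading. It does not close the gap: SAP 8.1.1 addresses Treatment Period 1 dropouts only, and a length of 1 day looks valid.
- **The handling may be in text not available here.** SAP 8.2 defers full derivation details to dataset specifications, and SAP 10.2.1 and 10.2.2 contain redactions. That is possible, but the formula in SAP 8.2.8 is stated in full and gives an invalid denominator as it stands.
- **Consent delays the switch.** SAP 4.3.2 requires consent first, and Protocol 12.3 requires re-consent. If consent at one visit means reduction at the next, consent at Day 119 gives a Day 147 switch and consent at Day 147 gives Day 231, with a normal 85-day window. The -27 case then needs consent before Day 119. This narrows the group but does not empty it.
- **Continuing subjects are not lost.** A reader might conclude that early switchers provide no efficacy data on the pre-reduction dose. That is wrong for subjects who continued on it from Treatment Period 1: they contribute to that period and to the combined window.
- **The stakes are limited.** The summaries are open-label and largely descriptive, and by-subject listings would expose odd values. This stands as to size.

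**Conclusion.** The defect is real but contained. As stated, the pre-reduction window has length -27 days for a Week 17 switch and 1 day for a Week 21 switch, and no visible rule says what to do with either. The reduced-dose portion separately counts up to 28 days in which attacks are excluded, 10% of the denominator for a Week 17 switcher completing at Day 399.

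These figures rest on nominal visit days; actual dates would shift them. The documents do not give the number of subjects reduced at or before Week 21, or show that there were any. A reader might estimate a share of the column from the planned allocations, but nothing in the documents supports a particular share. The primary Treatment Period 1 test, its alpha and its power are not affected.

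The allocation and reduction passages also do not fit together for subjects entering Treatment Period 2 after Amendment 2. They are allocated to a dose at Week 13 and reduced from it at the next scheduled visit, possibly before its efficacy window opens. The passages must be reconciled; no view is taken here on the dose rule.

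**What to change.** 1. **SAP 8.2.8, pre-reduction portion.** State that a subject contributes only if the planned reduction (or Study Completion) is after the Day 147 visit. Otherwise the subject is non-evaluable for that portion and listed only. No minimum length is needed, since the next nominal window is 85 days.
2. **Dependent tables.** Apply the same condition to the Treatment Period 2 rate, responder, attack-free and dose-comparison tables.
3. **SAP 8.2.8, reduced-dose portion.** Align the start of the denominator with the Week 13 to Week 21 attack exclusion, so that both cover the same days.
4. **Protocol.** The sponsor should reconcile sections 3.1.4 and 6.1.2 with 3.2.2 and 5.5 for C1-INH HAE subjects who enter Treatment Period 2 after Amendment 2.

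The cost is SAP wording, one derivation flag, an adjusted start date and a protocol clarification. Any early switchers leave the pre-reduction column, where they have no usable follow-up.
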